#### 7.4 Allowable Criteria

- has been using oral contraceptives, vaginal ring, or patch and is discontinuing the product to be enrolled
- has been using a contraceptive implant or IUD, but wishes to have the device removed prior to enrollment

# 7.5 Number of Subjects

The study is expected to enroll approximately 1100 female subjects randomized to one of the two IUDs.

CCN016 Version #: 03.00 Version Date: 19Dec2018 Page 21 of 76

#### 8 CONCURRENT MEDICATIONS AND TREATMENTS

#### **8.1** Allowed Medications and Treatments

Recording of all concomitant treatments will occur on the subject's source and electronic case report forms (eCRF), including the name of the drug, start and stop dates and reason for use from the time the informed consent form (ICF) is signed through discontinuation from the trial. Any other investigational product should be stopped at least 30 days before the start of screening for this trial. Other medications for the treatment of inter-current medical conditions will be permitted and recorded as detailed above unless identified on the exclusionary list of medications.

Condoms are allowed for protection from sexually transmitted infection (STI). However, anticipated regular use of condoms is exclusionary. Regular use of condoms is defined as an anticipated need of at least one condom per month after enrollment.

If a subject suspects that her IUD is not in place, she should return to the site as soon as possible for confirmation of IUD placement. In the meantime, she should use condoms during intercourse until she is evaluated by the site.

#### **8.2** Prohibited Medications and Treatments

Concomitant medications that should not be used during the study include:

- Exogenous hormones, including hormonal contraceptives, except if needed for medical reasons and used in a single cycle during the study
- Therapeutic anticoagulants (at enrollment only)

#### 9 STUDY TREATMENTS

# 9.1 Method of Assigning Subjects to Treatment Groups

The study will randomly assign approximately 1100 eligible participants to Mona Lisa NT Cu380 Mini or ParaGard in a 4:1 ratio using a SAS-based computer-generated randomization scheme. Randomization will be stratified by parity (nulliparous and parous will be the stratification categories with a goal of enrolling 80% nulliparous). Enrollment will be tracked to ensure approximately 10% of women are 36-40 years old.

The randomization listing will be uploaded to the HD EDC system for proper stratified randomization. The IUDs for each site will be provided in bulk and clinicians will pull the product from the existing stock based on the product identified in the EDC system at time of randomization.

Health Decisions will hold the randomization listing in a secure limited access location for the duration of the study.

Sites will enter the kit and randomization number provided from the EDC system on their IP dispensing log for each subject. The subject identification number assigned to subjects during the screening visit will identify them for the duration of the study.

CCN016 Version #: 03.00 Version Date: 19Dec2018 Page 22 of 76

# 9.2 Blinding (participant only)

The identity of the assigned IUD will not be shared with participant from the time of insertion through the Exit/37-month study visit. However, the clinicians inserting the product and clinicians conducting follow-up exams will know which product was assigned. Clinic staff completing other assessments should remain blinded as much as possible.

Sites will ensure single-blind administration of study treatments using the following study procedures:

- Once the product assignment is determined, study staff will prepare the IUD and supplies outside the view of the participant
- The study staff will pull the IUD from the stock and place all identifying packing information out of the sight of the subject (Note: all packaging materials should be retained in a secure location for examination and accountability by the monitor)
- If necessary, an overlay will cover the tray (or insertion supplies when not used on a tray) to prevent inadvertent unblinding to the study participant.

When the participant returns for follow-up, the participant blinding is to be maintained. The site will break the blind for the study participant on completion of her study participation at the Exit visit after all IUD assessments have been performed. During the study, the participant blind may be broken **only** in emergencies when the patient or treating physician must know which product was received. When possible, the Investigator should discuss the emergency with the Medical Monitor prior to unblinding. As outlined in Section 12.1, subjects should be instructed to contact the study site to report any untoward medical occurrence that they experience. If health care is received elsewhere, for any reason, the participant should inform the attending clinician of their study participation request that no details of their IUD be shared.

#### 9.3 Formulation of Test and Control Products

The products used in this study are the ones that are marketed in the USA and in Europe.

#### 9.3.1 Formulation of Test and Control Products

Table 01. Formulation and the Test IUDs

	Control Product	Test Product
	ParaGard	Mona Lisa NT Cu380 Mini
Manufacturer	Teva Pharmaceutical, USA	Mona Lisa, N.V.
		Belgium
Active ingredient	Copper	Copper
	380mm  surface area	380mm  surface area
Copper purity	>99.95%	>99.95%
Frame	Polymer	Polymer
Free state shape	"T" shape	"T" shape

CCN016 Version #: 03.00 Version Date: 19Dec2018 Page 23 of 76

	Control Product	Test Product
Frame dimensions	32mm x 36mm	24mm x 30mm

#### 9.3.2 Packaging and Labeling

All labeling of the study product will be prepared in accordance with 21CFR, Section 812.5. Study product will be supplied in the original manufacturer packaging containing a single use IUD with a study label applied on the original packaging for study purposes. The study label will provide the study specific information as follows:

- Protocol Identification: CCN016
- Sponsor Identification: NICHD/FHI 360
- Kit Number (preprinted/space to record)
- Subject ID (space to record)
- Subject Initials (space to record)
- Date Dispensed (space to record)
- FDA Caution Statement: CAUTION -- Investigational drug. Limited by Federal (or United States) law to investigational use.
- Distributor: FHI 360, [name]
- Directions: Use as Directed in CCN016 Protocol.
- Storage: Controlled Room Temperature (15 to 30°C (59 to 86°F))
- Keep Out of Reach of Children

# 9.4 Provision of Study Product to Participants

At the study site, the Principal Investigator (or designee) will insert the IUD into the participant's uterus during the enrollment visit. If insertion is not successful on the first attempt, a second attempt with the same product may be made during the enrollment visit only. If second attempt is unsuccessful then the subject will be discontinued.

Once successfully inserted, the IUD will remain in place for up to 37 months for current study purposes unless product expulsion occurs, safety concerns arise or the subject chooses to have the IUD removed prior to completion of 37 months of use for any reason. No replacement of study IUDs will occur should product expulsion or accidental removal occur. If expulsion or accidental removal occurs prior to 37 months of continuous use, subjects should contact the study site immediately to be scheduled for an Exit Visit.

#### 9.4.1 Dosage Regimen

Subjects will be enrolled and randomized to receive one of the copper IUDs being studied. The single IUD will be inserted in the uterus by delegated study staff at a subject's enrollment visit.

### 9.4.2 Dispensing

The Principal Investigators (or designees) have authority to retrieve the IUDs from the temperature controlled, secure limited access stored supply stock.

Prior to dispensing, the Principal Investigator or designee will record the site number, subject's identification number, initials, and date dispensed on the overlay packaging. Upon dispensing, the original manufacture packaging should be replaced within the overlay packaging for monitoring accountability purposes.

The Principal Investigator (or designee) will record the randomization number, subject identification number, subject initials, and date dispensed on the accountability log.

#### 9.4.3 Administration Instructions

This is a single-blinded study; the participant should not see the assigned IUD or the manufacturer's product packaging. Precautions should be taken to prevent subjects from seeing the manufacturer's product packaging, including but not limited to covering the IUD and insertion supplies with a sterile overlay to prevent inadvertent unblinding.

Each IUD has an FDA- or European-approved product label that contains insertion instructions. Training will occur for Investigators on proper insertion technique for the test product. Investigators can also refer to the product label and Investigator's Brochure for additional information.

All pre-insertion clinical assessments are the same for all IUDs as described in Sections 11.1.1 Screening Procedures and 11.1.2 Enrollment Procedures.

# 9.5 Supply of Study Product at the Site

Health Decisions will oversee the shipment of Study Product to the investigational sites. Shipment of the initial study product will occur after site authorization (i.e., all required regulatory documentation has been received by the Sponsor, IRB approval has been received and a contract has been executed). Once a site request for resupply is received, shipment of subsequent study product will occur.

#### 9.5.1 Storage

Study product should be stored in a dry place at the study site at controlled room temperature, 15 to 30°C (59 to 86°F) under controlled and secured conditions (in a locked storage area away from sunlight). A temperature log for the investigational product storage area must be maintained for the duration of the study. If the temperature of the study product storage area exceeds or falls below the allowable range, this should be reported to the Sponsor or designee and captured as a deviation.

#### 9.6 Study Product Accountability

An accurate and current accounting of the dispensing, insertion, and removal of study product for each subject will be maintained on an ongoing basis by a member of the study site staff. Recording of information regarding study product disposition will occur on the Investigational Product Accountability Log by Investigator (or designee). The study monitor will verify these documents and product packaging on a regular basis throughout the course of the study. Refer to Section 9.4.2 for some of the information that dispensing staff will capture on the Accountability Log. After documented accountability has been completed for a subject by the monitor, the site may dispose of the used study product and/or product overlay packaging per Section 9.8.

CCN016 Version #: 03.00 Version Date: 19Dec2018 Page 25 of 76

# 9.7 Measures of Treatment Compliance

Compliance with treatment is a key endpoint of the study; this status is documented by verifying that the IUD is in situ. To verify the presence of the IUD, the clinician will check for the IUD string at each study visit (refer to **Appendix 2** for confirmation process). If the IUD string is not visible or palpable on examination, or if there is clinical suspicion of expulsion, clinicians will proceed with ultrasound and x-ray examination (if appropriate) to verify that the IUD is in position. Should IUD be removed outside of the site, the Investigators should request release of medical records by subject upon notification if removal was completed by a non-study medical provider or proceed with verification steps in Appendix 2 to confirm removal if completed by the subject. For this study, we will use the following definitions:

- 1. Complete expulsion: the IUD is completely outside of the uterus and cervix, as evidence by seeing the IUD outside the uterus or complete absence of the IUD on ultrasound examination with no evidence of an intraabdominal IUD by X-ray;
- 2. Partial expulsion: visualization or palpation of any portion of an IUD (other than strings) at the cervical os, or ultrasound identification of any part of the IUD in the cervical canal, regardless of symptoms.

# 9.8 Study Product Disposal/Return

At the end of the study, the monitor will complete a final accountability of all clinical supplies, including remaining unused product and used product overlay packaging. Remaining used (e.g., removed or expelled) study product destruction will occur on-site following site-specific destruction standard operating procedures once monitor accountability has been completed. Guidance for remaining unused study product return or disposal will be provided by the Sponsors at the end of the study.

#### 10 STUDY PROCEDURES AND GUIDELINES

#### 10.1 Investigator's Meeting and Protocol Training

Prior to initiating recruitment of participants, an Investigator's Meeting will be held for the following purposes:

- To train Investigators on proper insertion of the test product
- To train Investigators on the protocol specifics and study manuals
- To document training
- To train on other study specific requirements

#### 10.2 Clinical Assessments and Procedures

A Schedule of Assessments representing the required testing procedures to be performed for the duration of the study is diagrammed in Appendix 1.

Prior to conducting any study-related activities, written informed consent and the Health Insurance Portability and Accountability Act (HIPAA) authorization must be signed and dated by the subject or subject's legal representative. If appropriate, assent must also be obtained prior to conducting any study-related activities.

# 10.2.1 Medical, Demographic, and Reproductive Health History

At the screening visit, study staff will ask women about their medical and gynecologic history, including specific questions about any medical problems or current medications that may be contraindications to the use of any of the study methods. Women will also be asked about their past use of contraceptive methods as relevant and details about their previous pregnancies, if any. General subject demographic information (i.e. race, ethnicity, level of education, etc.) will also be collected at screening.

#### 10.2.2 Vital signs and Pelvic Exam

Trained research staff will collect vital signs on all potential participants at screening to evaluate for contraindications to the study methods. These exams will include measurement of blood pressure, height, and weight, and a pelvic exam, including speculum exam. A bimanual exam will be done to assess for the presence of any uterine or cervical anomalies, possible pelvic infection, or other abnormal findings such as an adnexal mass that would preclude IUD use. An assessment of uterine cavity length also will be completed by sound or pipelle while speculum is still in place after the subject is randomized but prior to IUD insertion. Any suspected reproductive tract infections (RTI) identified on physical exam will be diagnosed and treated according to local standards of care. Enrollment will be deferred pending treatment. In addition, treatment will be initiated and/or adjusted as appropriate based on laboratory results when available and include treatment of sexual partners when indicated. If an infection is suspected or confirmed, treatment according to the site's standard of care is indicated. Once treatment is complete, the subject may return for continued screening and may be enrolled within a month of the start of screening if there is no obvious sign of infection. If no infection is suspected at time of screening, subjects may enroll the same day.

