If enrollment cannot proceed for any reason, including a contraindicated infection or immediately post abortion/delivery, the potential participant should return no later than 60 days from the start of screening to be enrolled. If the potential participant was treated for a sexually transmitted infection, treatment should be complete and there should be no signs of active infection prior to enrollment. If the potential participant appears to have been re-infected, she would be considered a screen failure. If the potential participant was screened less than 30 days post-abortion or delivery, confirmation of eligibility should be completed prior to randomization including review for any new history, review of concomitant medications and urine pregnancy check. Review of cases that require a screening period longer than 60 days will occur on a case by case basis through a submitted waiver. If the enrollment visit occurs separately from screening, sites will reconfirm study eligibility prior to enrollment, including pregnancy testing. Study staff will collect adverse events (AEs) and any new or changed concomitant medications. Sites will randomize eligible women (at which point a woman will be considered enrolled) and women will receive one of the two study IUDs. Once enrolled, reimbursement for the women's time and scheduling of their 6-week contraceptive follow-up visit will occur.

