**Table 03: Enrollment Visit Procedures** 

Component	Procedures
Administrative and Regulatory	
 
Randomize subject in EDC system and record required information on study product label
 

	
 
Provide reimbursement
 

	• Schedule next study visit (6 weeks out ± 5 days)
	
 
Review diary cards, including proper completion instructions. Distribute 2 daily diary forms; each form covers a 1-month period
 

CCN016 Version #: 03.00 Version Date: 19Dec2018 Page 32 of 76

Clinical	
 
If visit is separate from screening, reassess eligibility, including infection status, if treated, and risk of pregnancy
 
Assess for AEs and concomitant medication
 
Complete assessment of uterine cavity length by sound or pipelle. If cavity length measures less than 5.5 cm, subject must be discontinued and insertion should not be completed.
 
Collect information on subject's pain after speculum placement and prior to sounding of the uterus (baseline pain assessment)
 
Insert assigned IUD
 
Assess ease of insertion
 
Collect information on subject's pain after insertion (immediately and 10 minutes after insertion)
 

	
 
Insert assigned IUD
 
Assess ease of insertion
 
Collect information on subject's pain after insertion (immediately and 10 minutes after
 

	
 
Distribute Home Post Placement Pain Form for subjects to record their maximum daily pain for the 6 consecutive days following IUD placement, satisfaction with IUD and use of pain medications.
 

Laboratory Urin	e Test urine for pregnancy
5	• Retest for STIs if needed

**Note:** If enrollment does not immediately follow the screening procedure, confirmation of eligibility must be performed using clinical judgement to decide whether repeat pregnancy, STI testing, or other assessments are needed and if contact information should be reviewed. In addition, collection of information on AEs and concomitant medication changes will occur.

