# 15.3 Replacement of Subjects

Subjects who withdraw from the study treatment or withdraw from the study will not be replaced, regardless of the reason for discontinuation.

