5.3. Treated Population

The Treated Population is a subset of ITT Population and includes only participants who advanced to uterine sounding, had their uterus successfully measured, and then underwent an attempted IUD insertion procedure. Inadequate uterine depth (at least 5.5cm) and/or medical contraindication (such as mucopurulent discharge discovered before/during/after sounding) are examples of situations that exclude participants from the Treated Population. Participants who received the incorrect IUD are included in this population and analyzed according to the treatment they actually received. This analysis population will mainly be used for evaluating insertion results and safety and other secondary endpoints observed during the insertion process. Participants' baseline characteristics will be analyzed only if more than 5% of the ITT Population are excluded from the Treated Population.

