7.6.1 Exiting the trial before attempting IUD insertion

The ITT Population will be used for estimating the incidence of exiting the trial before attempting an IUD insertion. Reasons for exiting the trial before attempting IUD insertion include:

- Could not sound the uterus
- Shallow uterine depth (less than 5.5cm)
- Medical contraindication discovered post-randomization but before IUD insertion attempt

The frequency and the percentage of women who exited the trial for different reasons before IUD insertion will be tabulated by treatment group and by study site. The proportions of participants experiencing these events will be calculated with corresponding exact confidence intervals for each group, and the difference between the groups will be compared using the Cochran-Mantel-Haenszel tests.

7.6.2 IUD successful insertion, failed IUD insertion, and incident adverse events during the insertion process

The Treated Population will be used for evaluating the incidence of successful IUD insertion and incident adverse events (e.g., perforation) occurred during the insertion process. The frequency and the percentage of women who experienced IUD placed successfully at the first attempt, at the second attempt, and incident adverse events occurred during the insertion process will be tabulated by treatment group and by study site. The proportions of participants experiencing these events will be calculated with corresponding exact confidence intervals for each group, and the difference between the groups will be compared using the Cochran-Mantel-Haenszel tests.

7.6.3 IUD expulsions, incident adverse events, and other events after a successful IUD insertion

The User Population will be used for analysis of IUD expulsions (complete and partial), incident adverse events, and other events. For each adverse effect (e.g., PID or uterine perforation), two measure units will be used in this analysis: 1) number of participants experiencing at least one adverse effect and 2) number of the AE reporting during the study. First, the proportions of participants experiencing the AE will be calculated using exact confidence intervals for each group and compared between groups using Fisher's exact tests or the Cochran-Mantel-Haenszel tests. Secondly, generalized linear models with GEE for repeated AE outcomes will be used to further explore the differences in the incidence of AEs between study groups.

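### Uterine sounding and the 5.5 cm limit act as eligibility checks but come after randomisation, so the secondary comparisons rest on subsets that can be selected differently by arm

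*Protocol*

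**What the plan says.** **Order of steps.** Protocol 10.2.2: "An assessment of uterine cavity length also will be completed by sound or pipelle while speculum is still in place after the subject is randomized". Protocol 11.1.2 makes randomisation the moment of enrolment: "Sites will randomize eligible women (at which point a woman will be considered enrolled". Table 03 sets the consequence of a short cavity: "If cavity length measures less than 5.5 cm, subject must be discontinued and insertion should not be completed". Neither 7.2 nor 7.3 contains a depth or sounding criterion.

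**Knowledge of allocation.** Protocol 9.1: "clinicians will pull the product from the existing stock based on the product identified in the EDC system at time of randomization". Protocol 9.2 adds that "the clinicians inserting the product and clinicians conducting follow-up exams will know which product was assigned".

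**Replacement.** Under Protocol 15.3, women who withdraw "will not be replaced, regardless of the reason for discontinuation".

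**Analysis sets.** SAP 5.3 says that inadequate depth and contraindications such as discharge found around sounding "are examples of situations that exclude participants from the Treated Population". The User Population (SAP 5.4) is a subset of Treated, and the Efficacy Analysis Population (SAP 5.6) is a subset of User. SAP 5.2 keeps these women in ITT, but uses ITT mainly for baseline tables.

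**What is already planned for these exits.** SAP 7.6.1 tabulates exits before any insertion attempt in ITT, by arm and site, with exact confidence intervals and a Cochran-Mantel-Haenszel test. The reasons are an unsuccessful sounding, shallow depth and "Medical contraindication discovered post-randomization but before IUD insertion attempt".

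**The concern.** The depth limit and the ability to sound do not depend on the assigned device, so they could be settled before allocation. Placed afterwards, they let judgement made with the device known decide who enters the comparison. Reading a sound near the limit, abandoning a difficult sounding and calling a finding a contraindication all involve judgement.

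The appended material gives a reason for that judgement to differ by arm. The ParaGard label (Appendix 7) gives a sounding range of 6 to 9 cm and warns of more complications below 6 cm. The test-product insert, as reported in Protocol 2.1.2, describes cavities under 7 cm. The protocol applies 5.5 cm to both.

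At stake are the randomised secondary comparisons: failed insertion, ease of insertion, insertion pain and continuation. The control arm has only about 220 women and insertion events are likely to be few, so a handful of selective exits matters more there.

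**Working it through.** **1. Where the exits go.**

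| Comparison | SAP section | Population | Contains pre-attempt exits? |
|---|---|---|---|
| Exit before attempt | 7.6.1 | ITT | Yes |
| Successful or failed insertion | 7.6.2 | Treated | No |
| Ease of insertion | 7.6.5 | Treated | No |
| Pain | 7.6.4 | Treated (baseline), User (all 9 measures) | No |
| Discontinuation | 7.4 | User | No |

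The classification table in SAP 7.4.1 lists, as discontinuation reasons, a uterus that was not sounded or was too short, and a failed placement attempt. The User Population by definition contains neither group, so these reasons cannot occur in the Kaplan-Meier and log-rank analyses of 7.4.2. Protocol 19.2.2 lists failed insertion among the reasons to be compared. No planned analysis compares, as randomised, the chance of leaving the enrolment visit with a device successfully placed.

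**2. Reproducing the plan's figures (Protocol 19.1, 800 test women).**
- Inputs: 13 cycles per year, 84.3% evaluable, 20% discontinuation per year (h = -ln 0.8 = 0.2231), 37 months, and about 90% under 36 (Protocol 9.1).
- Cycles = 800 x 0.90 x 13 x 0.843 x (1 - exp(-h x 37/12))/h = 7,890.5 x 2.229 = 17,590, within 0.6% of the stated 17,700.
- Upper bound with 6 pregnancies (SAP 7.3.2) = 26.119 x 1300/(2 x 17,700) = 0.96, stated as about 1.0.
- Log-rank power: 190 v 760 after 5% loss gives 190 x 0.30 + 760 x 0.20 = 209 events; HR = ln 0.8/ln 0.7 = 0.626. Freedman's formula, z = sqrt(209 x 4) x (1 - 0.626)/(1 + 4 x 0.626) - 1.96 = 1.13, gives 87.1%, matching 87%.

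These figures reproduce with every randomised woman contributing follow-up. Nothing is deducted for exits at sounding.

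**3. Loss of exposure at the current size (880:220).** Cycles scale to 17,700 x 880/800 = 19,470. The exit rates are assumptions, taken as equal in both arms.

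| Exit rate | Women lost (test, control) | Cycles | Upper bound, 6 pregnancies | Power |
|---|---|---|---|---|
| 0% | 0, 0 | 19,470 | 0.87 | 90.0% |
| 1% | 8.8, 2.2 | 19,275 | 0.88 | 89.7% |
| 5% | 44, 11 | 18,497 | 0.92 | 88.5% |
| 10% | 88, 22 | 17,523 | 0.97 | 86.8% |

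**4. Differential selection in continuation.** Let q be the 12-month continuation that excluded women would have had if inserted. Continuation seen in User = (true rate - exit rate x q)/(1 - exit rate). With true rates of 80% and 70%, and exits of 2% (test) and 5% (control):
- q = 50%: test (0.80 - 0.010)/0.98 = 80.6%; control (0.70 - 0.025)/0.95 = 71.1%; difference 9.6 points.
- q = 30%: 81.0% v 72.1%, difference 8.9 points.
- q = 70%: 80.2% v 70.0%, difference 10.2 points.

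With exits of 2% v 10% and q = 50%, the difference is 8.4 points.

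**5. Would SAP 7.6.1 detect it?** By an unstratified normal approximation at 220 v 880, power is about 59% for exits of 3% (control) v 1% (test), and about 66% for 5% v 2%. A large imbalance would show; a modest one could be missed.

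**The case against.** **The primary result.** A reader might infer that the efficacy estimate is biased by arm, or that its upper bound is pushed past 1.0. The documents do not support this. The Pearl Index is estimated in the test arm, and SAP 7.3 rules out formal comparisons between the efficacy groups. The bound with 6 pregnancies passes 1.0 at 5% exits only on the superseded 800 women (0.959/0.95 = 1.01). At 880 it stays below 1.0 even at 10%.

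**The exits are not hidden.** SAP 7.6.1 compares them by arm in ITT, and SAP 7.1 adds a flowchart and reasons for non-inclusion in each population. This stands: an imbalance would be visible, subject to the power above. Visibility does not repair the comparisons made in Treated and User.

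**The sounder's knowledge is inferred.** Protocol 9.2 speaks of the clinician inserting the product. That the same person sounds, already knowing the device, is plausible from 9.1, 10.2.2 and Table 03 but is not stated. The firm point is that no step prevents it.

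**Infection.** One might read the plan as first looking for infection after randomisation. It does not: Protocol 7.3 requires no obvious signs on pelvic exam at enrolment, and 11.1.2 requires eligibility to be reconfirmed when enrolment is on a separate day. Only findings missed at that check remain.

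**The as-randomised contrast has its own weakness.** Exits unrelated to the device dilute it: with 5% exits in both arms, a 10-point difference among inserted women becomes 0.95 x 10 = 9.5. If exits are selective, it charges them to the arm: in the 2% v 5%, q = 50% case it gives 79.0% v 67.5%, or 11.5 points. It is a sensitivity analysis beside the planned one, not a recovery of the true difference.

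**Timing.** Recruitment was expected to end in Q1 2019 and protocol version 3.0 is dated December 2018, so reordering the visit may reach few women unless enrolment was extended.

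**Conclusion.** The point holds for the randomised secondary comparisons, as a worthwhile improvement and not a threat to the primary result. An arm-independent eligibility check sits after randomisation, allocation is not concealed from the person sounding, and the main secondary analyses use populations formed after that step. The listed discontinuation reasons also do not fit the population in which discontinuation is analysed.

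The size depends on exit rates that the documents do not give. Under the assumed 2% v 5% exits, a true 10-point continuation difference would appear as 8.9 to 10.2 points for q from 30% to 70%. The documents give no insertion-failure rate, so the effect on that comparison cannot be sized. For the primary estimate the effect is a small loss of exposure, about 0.87 to 0.92 on the upper bound at 5% exits, with 880 women and 6 pregnancies. The documents do not show that selective exits occurred; they show that the design permits them.

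**What to change.** 1. **SAP 7.6.2 and 7.4.** Add two as-randomised ITT sensitivity comparisons beside the planned Treated and User analyses: the proportion with no device successfully inserted at the enrolment visit, and continuation with pre-attempt exits and failed insertions counted as events at time zero. Align the reason list in 7.4.1 with the population used for each analysis. The data are already collected, so the cost is one or two tables and a contrast somewhat diluted by device-independent exits.

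2. **Protocol 10.2.2, Table 03 and Appendix 1, for any women still to be enrolled.** Move the existing sounding and depth check ahead of EDC randomisation, so that women who do not pass become screen failures. Alternatively, withhold the allocation from the person sounding until the result is recorded. This adds no procedure. The cost is a protocol amendment and a short delay with the speculum in place, and reordering means slightly more women screened.

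3. **Reconcile the depth figures.** The sponsor should reconcile the protocol's cut-off with the depth ranges in the appended labels, and the 5.5 mm in the footnote to SAP Appendix A with the 5.5 cm in SAP 5.3.
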